6.5.1 Receipt of COVID-19 Vaccines During the Study

Individual participants are encouraged to receive a COVID-19 vaccination when they become eligible and it is locally available. If a participant plans to receive a COVID-19 vaccine within 14 days of study Day 1 (AZD7442 administration) they should delay starting in the study until > 14 days after their last dose of vaccine (Section [5.2](#)). Available data suggests that AZD7442 may provide 6 months of protection against pre-Omicron SARS-CoV-2 variants but due to a reduced in vitro neutralization against the Omicron variant, AZD7442 may provide a different duration of protection against Omicron. Protection has not yet been demonstrated in children.

Theoretically, in the presence of adequate neutralizing antibody titers, expected for the durations noted, an appropriate and effective response to the vaccine could be impaired. Data from animal studies reported that prior AZD7442 administration did not alter either the cellular or the humoral immune responses elicited by subsequent COVID-19 vaccinations. Based on these results, AZD7442 is not anticipated to interfere with vaccine efficacy. If the participant decides to receive the vaccination the participant can proceed and continue in the study. If a participant has a breakthrough case of COVID-19 during the study despite being previously vaccinated, they should be managed using standard of care.

For participants who have received IMP and develop symptomatic COVID-19 at some point in the study:

- There is no reason to believe that administration of a vaccine during acute COVID-19 illness will ameliorate the illness.
- In most mAb recipients, an infection-induced immune response will occur, and this response should be protective.
- The risk associated with receiving a vaccine after resolution of the illness should be low.

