7.4 Stopping Rules, Progression to Next Study Part, and Termination of Study

7.4.1 Stopping Rules for an Individual Participant, at Any Time in the Study

Each participant in this study will receive a single dose of IMP. An individual participant will not receive IMP if any of the following occur in the participant in question:

- Withdraws consent after signing informed consent.
- Meets one or more of the exclusion criteria or fails to meet all inclusion criteria for study participation.

Each participant who has received IMP will be followed for the full study period unless consent is withdrawn specifically from further study participation, or the participant is lost to follow-up. Participants who have not received IMP, regardless of reason, will not be followed. Unless consent for follow-up is withdrawn, participants discontinued after receiving a partial dose of IMP will be followed for the full study period (up to and including Day 366, 52 weeks after IMP dosing) with all laboratory and clinical evaluations collected as defined in this CSP.

7.4.2 Stopping Rules for a Whole Cohort, Progression to Next Study Part, and Termination of Study

The Sponsor reserves the right to temporarily suspend or permanently terminate this study or a component of the study at any time.

Stopping rules as detailed below (general, cardiovascular, laboratory, and AZD7442 specific).

General Criteria

The study will be put on temporary hold (defined as stop of enrollment of participants into the study) pending further safety data analysis if any of the following criteria occur in participants receiving AZD7442:

- An SAE (including death) where there is a reasonable possibility that it is related to the IMP administration in any one participant.
- A severe non-serious adverse reaction where there is a reasonable possibility that it is related to the IMP administration in 2 or more participants in the same cohort, independent of, within, or not within the same system organ class.

The risk to all participants will be evaluated thoroughly prior to a decision as to whether to terminate the study prematurely or continue dosing in agreement with the regulatory authorities.

The DSMB will carefully review the totality of data, taking into account moderate non-serious AEs where there is a reasonable possibility that the AE is related to the IMP administration, the number of participants in which the AE occurs, and concurrency of more than one AE within the same participant.

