9.3 Populations for Analyses

The analysis populations are defined in [Table 17](#).

Table 17 **Populations for Analysis**

Population/Analysis Set	Description
Screened population set	All participants who signed the ICF. Unless otherwise stated, the enrolled set will be used for the presentation of disposition data.
Full Analysis Set	All participants who received IMP, irrespective of their protocol adherence and continued participation in the study. Participants who withdraw consent or assent to participate in the study will be included up to the date of their study termination.
Safety Analysis Set	All participants who have received IMP.
PK Analysis Set	All participants who received AZD7442 and from whom PK blood samples are assumed not to be affected by factors such as protocol violations, and who had at least one quantifiable serum PK observation post-dose, will be included in the PK analysis dataset.
ADA Evaluable Analysis Set	All participants who are AZD8895 ADA evaluable and/or AZD1061 ADA evaluable. A participant is AZD1061 ADA evaluable if they are in the Safety Analysis Set and have a non-missing baseline AZD1061 ADA result and at least one non-missing post-baseline AZD1061 ADA result. A participant is AZD8895 ADA evaluable if they are in the Safety Analysis Set and have a non-missing baseline AZD8895 ADA result and at least one non-missing post-baseline AZD8895 ADA result.
SARS-CoV-2 nAb Evaluable Analysis Set	All participants in the Safety Analysis Set from whom blood samples were assumed not to be affected by factors such as protocol violations and who had at least one quantifiable serum titer observation post dose.

ADA, anti-drug antibodies; COVID-19, coronavirus disease 2019; ICF, informed consent form; IMP, investigational medicinal product; nAb, neutralizing antibody; PK, pharmacokinetic, SARS-CoV-2, severe acute respiratory syndrome coronavirus 2.

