**Table 1: Analysis sets**

Population/Analysis Set	Description
Screened Population Set (SPS)	All participants who signed the ICF. Unless otherwise stated, this set will be used for the presentation of disposition data.
Full Analysis Set (FAS)	All participants who received the IMP, irrespective of their protocol adherence and continued participation in the study. Participants who withdraw consent or assent to participate in the study will be included up to the date of their study termination.
Modified Full Analysis Set (mFAS)	All participants who are in the FAS, excluding participants who were assigned to Cohort 1 by rapid COVID-19 test, but have a positive confirmatory test.
Safety Analysis Set (SAF)	All participants who have received IMP.
PK Analysis Set (PKS)	All participants who received AZD7442 and from whom PK blood samples are assumed not to be affected by factors such as protocol violations, and who had at least one quantifiable serum PK observation post-dose, will be included in the PK analysis dataset.
AZD1061 ADA Evaluable Analysis Set (ADS1)	A participant is AZD1061 ADA evaluable if in the SAF and having a non-missing baseline AZD1061 ADA result and at least one non-missing post-baseline AZD1061 ADA result.
AZD8895 ADA Evaluable Analysis Set (ADS2)	A participant is AZD8895 ADA evaluable if in the SAF and having a non-missing baseline AZD8895 ADA result and at least one non-missing post-baseline AZD8895 ADA result.
AZD7442 ADA Evaluable Analysis Set (ADS3)	All participants who are AZD8895 ADA evaluable and/or AZD1061 ADA evaluable.
SARS-CoV-2 nAb Evaluable Analysis Set (SES)	All participants in the Safety Analysis Set from whom blood samples were assumed not to be affected by factors such as protocol violations, and who had at least one quantifiable serum titer observation post dose.

Generally, all listings will be prepared based on the SAF unless otherwise stated.  
Disposition data will be listed for the SPS.

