**Table 2: Analysis Endpoints**

Objectives	Endpoints	Analysis Set
Primary		
To evaluate the serum concentrations of AZD7442 after a single IM or IV dose in pediatric participants	Serum concentrations of AZD7442 at specified time points during the one-year study period when administered as a single IM or IV dose  Serum PK parameters (if data permits): Cmax, tmax, t1/2, AUC0-last , AUC0-inf , tlast, %AUCext, and: 

• for IM: CL/F, and Vz/F

• for IV: CL, and Vss

 Model-derived predicted serum AZD7442 concentrations, Cmax and AUC0-inf	PKS
To evaluate the safety and tolerability of AZD7442 after a single IM or IV dose in pediatric participants	TEAEs, SAEs, and AESIs (including anaphylaxis, injection/infusion site reactions, MIS-C).  Safety laboratory parameters (hematology, clinical chemistry, coagulation, and urinalysis); 12 lead safety ECG; vital signs (BP, pulse rate, tympanic membrane temperature, and respiratory rate), and physical examination.	SAF
Secondary – All Cohorts		

Objectives	Endpoints	Analysis Set
To evaluate the PD of AZD7442 after a single IM or IV dose	Titer of SARS-CoV-2 neutralizing antibodies	SES
To evaluate the immunogenicity profile of AZD7442	Incidence of ADA and nAb to AZD7442 in serum	ADS1/2/3
Secondary – Cohort 1 (Prophylaxis)		
To evaluate the incidence of SARS-CoV-2 infections with or without COVID-19 symptoms after a single IM or IV dose of AZD7442 in pediatric participants	Incidence of SARS-CoV-2 infections with and without COVID-19 symptoms	SAF, mFAS
Secondary – Cohort 2 and Cohort 3 (Treatment)		
To quantify SARS-CoV-2 viral loads after a single IM or IV dose of AZD7442 in pediatric participants	Change from baseline to Day 8 in viral load as measured by qRT-PCR.	SAF
To evaluate the proportion of participants with progression of COVID-19 after a single IM or IV dose of AZD7442 in pediatric participants	Proportion of participants with progression of COVID-19 through Day 29	SAF
To evaluate COVID-19 related death through 90 days after a single IM or IV dose of AZD7442 in pediatric participants	The incidence of COVID-19-related death occurring after dosing with IMP up to study day 90	SAF
Secondary – Cohort 3 (Severe COVID-19)		

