### **4.2.3 Secondary Endpoint – All Cohorts**

#### **4.2.3.1 SARS-CoV-2 neutralizing antibodies**

To evaluate the PD of AZD7442 after a single IM or IV dose, titers of SARS-CoV-2 neutralizing antibodies will be listed for the SAF and summarized for the SES at each time point.

Descriptive statistics for gmean titers (GMT) and geometric mean fold rises will include number of participants, gmean, gSD, 95% CI for the gmean, minimum, and maximum.

The GMTs for nAbs will be calculated for all participants in the SES as the antilogarithm of  $\Sigma(\log_2 \text{transformed titer}/n)$ , ieas the antilogarithm transformation of the mean of the log-transformed titer with base 2, where n is the number of participants with titer information. The gSD for GMT will be calculated as the antilogarithm transformation of the standard deviation of the log-transformed titer. The 95% CI will be calculated as the antilogarithm transformation of the upper and lower limits for a two-sided CI for the mean of the log-transformed titers.

Summary tables will be generated by cohort and route of IMP administration, and separately by cohort, route of administration and COVID-19 vaccination status at baseline (as captured in the eCRF).

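### The neutralising-antibody set requires a quantifiable post-dose titre, so a sampled child below the limit at every visit drops out of the titre summaries; if any such child exists, the GMT is biased upward

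*SAP*

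**What the plan says.** SAP Table 1 builds the SES from Safety Analysis Set (SAF) participants whose samples are assumed unaffected by factors such as protocol violations and "who had at least one quantifiable serum titer observation post dose". Protocol Table 17 (Section 9.3) has the same condition: "protocol violations and who had at least one quantifiable serum titer observation post dose".

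SAP Table 2 assigns the secondary PD endpoint, "Titer of SARS-CoV-2 neutralizing antibodies", to the SES and names no second set for it. SAP 4.2.3.1 states that "titers of SARS-CoV-2 neutralizing antibodies will be listed for the SAF and summarized for the SES at each time point". It adds that "The GMTs for nAbs will be calculated for all participants in the SES", "where n is the number of participants with titer information". The geometric SD, 95% CI and fold rises follow the same route. Tables are split by cohort and route, and again by baseline vaccination status.

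Three other places matter:

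- The ADA sets in SAP Table 1 need only non-missing results at baseline and after baseline, so a negative result keeps the child in.
- SAP 4.2.1.6 has rules for values below the limit of quantification, but they are written for serum drug concentrations. No rule covers below-limit titres.
- SAP 4.1.1.2 lists each child's set membership and gives set counts by cohort.

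**The concern.** A set used to summarise an outcome should not select on that outcome. Here a child with no measurable neutralisation at any post-dose visit, the clearest PD failure, leaves the denominator of the summary meant to describe PD response. Removing only low values moves the GMT in one direction.

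The endpoint is descriptive and carries no test, but it has a purpose. Protocol 4.2.1 says the PD markers will support the assumption that exposure-response is similar in children and adults, and losing the lowest responders favours that reading. Enrolment stopped early with 46 participants in the full analysis set (SAP Section 2). Neonates have no nAb sample (Protocol 8.5.1), and the tables are subdivided further. One excluded child could therefore be a visible share of a cell.

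**Working it through.** The plan states no expected GMT or precision for this endpoint, so there is no figure to reproduce. The check is a reading of the rule, one identity and some illustrations.

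**Who is removed.** Non-neonates have post-dose nAb samples at Days 31, 92, 183 and 366, or at early discontinuation (Protocol Table 3). The rule asks for at least one quantifiable value. A child quantifiable at Day 31 and below the limit later stays in; only a child below the limit on every available post-dose sample goes.

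**Direction.** Suppose k of n sampled children are never quantifiable and would be scored at a fixed value L. The log mean over all n is [(n − k)·log GMT(SES) + k·log L]/n, so

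GMT(SES) / GMT(all sampled) = (GMT(SES)/L)^(k/n).

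This exceeds 1 whenever k ≥ 1 and the SES GMT is above L, and equals 1 when k = 0.

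**Size for one excluded child.** Let R = GMT(SES)/L. R and the cell sizes are assumed; 46 is an upper bound on the nAb denominator if any neonates were dosed.

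| n (including the excluded child) | R = 4 | R = 16 | R = 64 |
|---|---|---|---|
| 46 | 1.03 | 1.06 | 1.09 |
| 20 | 1.07 | 1.15 | 1.23 |
| 10 | 1.15 | 1.32 | 1.52 |

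For example, 64^(1/46) = 1.095 and 64^(1/10) = 1.516.

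**Chance that it happens.** If a proportion q of children are never quantifiable, the chance of at least one exclusion among 46 is 1 − (1 − q)^46: 0.37 for q = 1% and 0.91 for q = 5%. The documents give no value of q.

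**Effect by visit.** A simulation took 46 children and the four visits, titres falling with a half-life of 366/4 = 91.5 days (from the four half-lives in Protocol 4.2.1), a between-child log2 SD of 1.5 to 2.0, visit-level noise of 0.5 on the log2 scale, and below-limit values at LLOQ/2. The table gives the SES GMT at Day 31 relative to all sampled children.

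| Assumed average titre at Day 31 | Ratio at Day 31 |
|---|---|
| 64 × LLOQ | 1.00 to 1.01 |
| 16 × LLOQ | 1.02 to 1.09 |
| 4 × LLOQ | 1.24 to 1.48 |

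At Day 366 the ratio was 1.06 or less in these scenarios, because most children below the limit by then had been quantifiable earlier.

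**Confidence interval.** Take n = 6, with one child 100-fold below the other five (log2 100 = 6.64) and an assumed log2 SD of 1 among the five. All limits are multiples of the five children's GMT.

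- Excluded: half-width 2.776 × 1/√5 = 1.24 on the log2 scale, so the limits are 0.42 and 2.36.
- Included: mean −6.64/6 = −1.11; SD = √[(4 × 1 + (5/6) × 6.64²)/5] = 2.86; half-width 2.571 × 2.86/√6 = 3.00; limits 0.06 and 3.71.

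Exclusion raises the GMT and the lower limit but takes the upper limit down from 3.71 to 2.36. With an SD of 2.0 the upper limit rises instead, from 4.93 to 5.59. The interval is narrower on the log scale in both cases.

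**The case against.** The best case against the point is that the excluded child may not exist. The product is itself a neutralising antibody. The first scheduled post-dose titre is at Day 31, when concentration is still high, so a child who leaves early would usually contribute the sample most likely to be quantifiable. Infection at baseline in Cohort 2 and permitted vaccination are further sources of antibody. This stands, and it makes the effect conditional.

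The child is also not concealed: all titres are listed for the SAF, and set membership and counts are reported. This stands too. The loss is confined to the summaries.

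The PK set in the same table uses the same at-least-one-quantifiable condition, and ADA is a positive/negative result for which non-missing is the natural criterion. So the contrast with the ADA sets does not prove an oversight. It does not change what the rule does to a GMT.

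Several stronger readings are tempting but not supported:

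- A reader might infer that partially dosed children make exclusion likely. SAP 4.1.3.1 counts deviations from planned dose as important deviations that may already remove a child from the SES, whatever the titre.
- A reader might infer the same from the "reduced in vitro neutralization against the Omicron variant" described in Protocol 6.5.1. That matters only if the assay uses such a strain, and the documents name none.
- A reader might infer that the whole confidence interval must shift upward. The working shows that its upper limit can move either way.
- A reader might infer that the exposure-response comparison is biased. Protocol 4.2.1 rests that comparison on the correlation of titre with concentration, and the SES is not specified for it.

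**Conclusion.** The point holds in conditional form. The SES rule selects on the outcome it summarises. If any sampled child is below the limit at every post-dose visit, the GMT is overstated and the interval may look more precise than it is. If there is no such child, nothing changes.

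The size cannot be established from the documents. The 3% to 10% (1 of 46) and 15% to 52% (1 of 10) rest on an assumed 4- to 64-fold gap and assumed cell sizes. If titres run far above the limit, the effect is negligible. This is a worthwhile, inexpensive correction to a descriptive secondary endpoint, not a threat to the trial's primary conclusions.

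**What to change.** In SAP Table 1, define the SES by at least one non-missing post-dose nAb titre result and keep the protocol-deviation clause. Record this in SAP Section 2 as a change from the protocol's planned analysis; Protocol 9.4.1 provides for such deviations to be described in the SAP.

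In SAP 4.2.3.1, state one prespecified value at which below-limit titres enter the log2 GMT and fold-rise calculations, at baseline as well as after dosing. LLOQ/2 is one option; LLOQ, as SAP 4.2.1.6 uses for drug concentrations, is another. Without such a rule it is unclear whether a below-limit result counts as titre information even for a child inside the SES. Report the number below the limit beside n at each visit.

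The cost is a line in the set definition, an entry in the list of changes, one programming rule and one extra table row. No new data are needed.

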#### **4.1.1.2 Presentation**

A listing will be provided presenting each subject's inclusion in each analysis set and cohort. The number of subjects in each analysis set will be summarized qualitatively by cohort.

### **4.1.2 Subject Disposition and Completion Status**

#### **4.1.2.1 Definitions and Derivations**

A clear accounting of the disposition of all participants who enter the study will be provided, from screening to study completion including potential re-screening.

For each subject, the dates for each visit they participated in will be listed.

#### **4.1.2.2 Presentation**

Participant disposition will be summarized and will include the following information: number of participants screened, randomized and dosed, number and percentage of participants completing the study and the number and percentage of participants who were withdrawn (including primary reason for withdrawal). The summary will be done overall and by cohort.

Participant discontinuations will be listed including the date of study exit, duration of participation and primary reason for discontinuation.

Participants and/or data excluded from the PK analysis set (see Section 4.1.1) will be listed including the reason for exclusion.

The analysis set to be used for these summaries and listings is the SPS (see Section 4.1.1).

#### **4.1.3 Protocol Deviations**

##### **4.1.3.1 Definitions and Derivations**

Important deviations from the protocol (IPDs) may lead to the exclusion of participants or data from the PKS or SES. Deviations will be assessed and classified during the study and finalized before database lock. IPDs include those deviations from the protocol that are likely to have an impact on the perceived safety of study treatments or outcome assessment.

IPDs will include the following at a minimum:

- Violation of key inclusion and/or exclusion criteria.
- Administration of prohibited concomitant medications that are expected to influence the outcome of this study.
- Deviations from planned dose or administration procedure of the IMP.
- Relevant time window deviations expected to influence key safety and/or PK assessments.

All important protocol deviations will be listed. A qualitative summary table will be provided.

##### **4.1.3.2 Presentation**

IPDs will be listed including the deviation type. The number of participants with IPDs will be summarized qualitatively by deviation type. The denominator for percentages will be the number of participants in the FAS.

#### **4.1.4 Demographics**

##### **4.1.4.1 Definitions and Derivations**

Demographics (age, age categories, estimated gestational age for prematurely born infants at birth, sex, race and ethnicity) will be listed and summarized for the SAF.

##### **Age**

A participant's age is captured during randomization in categories “ $\geq$  29 week gestational age to < 1 month”, “ $\geq$  1 month to < 1 year”, “1 year”, “2 years”, etc. to “17 years”. These categories will be integrated from the IRT into the study EDC system.

Additionally, for participants younger than 1 year, age in weeks (for age from 1 week to 3 months) or age in months (for age from four months to less than 1 year) will be captured. If the participant is prematurely born, the gestational age at birth in weeks is captured.

Age categories (1, 2, 3, 4, 4a and 4b) defined in Section 3.2 will be summarized by count and percent (relative to the number of participants in the analysis set) and age in years continuously for participants aged 0 to less than 12 years and 12 years or older separately.

In case transformations of units will need to be done, 4.3 weeks will amount to 1 month.

##### **4.1.4.2 Presentation**

The denominator for percentages will be the number of participants in the SAF. Summaries and listings will be done by cohort for the SAF.

Quantitative summary of age will be computed for each weight category separately.

A summary of demographics for those participants with a positively adjudicated Cardiovascular (CV) event will be presented.

